5.1 Imputation rules

5.1.1 AE date imputation

5.1.1.1 AE end date imputation

Rules for imputing AE end dates are stated below. Date of last contact in the study has been defined as in [Section 2.1.1.5](#).

1. If the AE end date month is missing, the imputed end date should be set to the earliest of the (date of last contact, 31DECYYYY, date of death).
2. If the AE end date day is missing, the imputed end date should be set to the earliest of the (date of last contact, last day of the month, date of death).
3. If AE year is missing or AE is ongoing, the end date will not be imputed.

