SAF	Safety Set
SAP	Statistical Analysis Plan
SAS	Statistical Analysis System
SBP	Systolic blood pressure
sCR	Serum creatinine
SD	Standard deviation
SOC	System Organ Class
SoC	Standard of care
T3	Triiodothyronine
T4	Thyroxine
TA	Transfusion avoidance
TBL	Total bilirubin
TEAE	Treatment emergent adverse event
TFLs	Tables, Figures, Listings
TSH	Thyroid stimulating hormone
ULN	Upper limit of normal
WBC	White blood cell(s)
WHO	World Health Organization

1 Introduction

The purpose of the document is to describe the statistical analyses to be included in the clinical study report (CSR) to be produced for submission at the time the last patient has completed the core treatment period in study CLNP023C12301. Hence the document covers the efficacy analysis on the core treatment period and the safety analysis on the data in the core treatment period, as well as the safety data in the extension treatment period collected till the data cut off for the submission of the CSR mentioned before.

An additional CSR will be produced when the last participant has completed the last visit in the extension treatment period, when the final study database has been locked. The statistical analyses for that CSR will be mentioned in a separate document.

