2.1.1.5 Completion and last contact

A patient will complete the core treatment period when the patient has completed the Day 168 visit in the study or EOS for participants who discontinue from the study prior to the extension treatment period. The maximum of the date of last visit in the core treatment period, date of withdrawal of consent (in case of withdrawal from study), would be the date of last contact for the patient in the core treatment period.

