 - c. Else if the AE month is equal to the treatment start date month or greater than the treatment start date month, the imputed AE start date is set to the later of (month start point (01MONYYYY), AE start reference date + 1 day).

If complete imputed AE end date is available and the imputed AE start date is greater than the imputed AE end date, then imputed AE start date should be set to the imputed AE end date.

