5.1.2 Concomitant medication date imputation

5.1.2.1 Concomitant medication end date imputation

Rules for imputing the CM end date are stated below. Date of last contact in the study has been defined as in [Section 2.1.1.5](#). Concomitant medication end dates will not be imputed for ongoing records.

1. If CM end day is missing and CM month/year are non-missing then impute CM day as the minimum of date of last contact and the last day of the month.
2. If CM end day/month are missing and CM year is non-missing then impute CM day as the minimum of date of last contact and the end of the year (31DECYYYY).
3. If CM day/month/year is missing then use the date of last contact + 1 day as the imputed CM end date.
4. If imputed CM end date is less than the CM start date, use the CM start date as the imputed CM end date.

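### Partial adverse event and medication end dates are capped at a last-contact date defined only for the core period, so some extension records are misdated

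*SAP*

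**What the plan says.** SAP Section 5.1.1.1 caps partial AE end dates. With the day missing, "the imputed end date should be set to the earliest of the (date of last contact, last day of the month, date of death". With the month missing, the end of the year replaces the end of the month. Two kinds of record are left alone: "If AE year is missing or AE is ongoing, the end date will not be imputed".

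For the cap, the section says "Date of last contact in the study has been defined as in" Section 2.1.1.5. That section takes "The maximum of the date of last visit in the core treatment period, date of withdrawal of consent (in case of withdrawal from study" and states that this "would be the date of last contact for the patient in the core treatment period". No extension or whole-study version is given anywhere in the SAP.

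Section 5.1.1.2 resolves a conflict between the two imputed AE dates by moving the start: "then imputed AE start date should be set to the imputed AE end date".

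Section 5.1.2.1 uses the same cap for medications ("impute CM day as the minimum of date of last contact and the last day of the month") but adds, as its rule 4, that an end earlier than the start is reset to the start. The AE end-date rules have no such guard.

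The SAP Introduction puts extension records within scope: the document covers core safety data "as well as the safety data in the extension treatment period collected till the data cut off". Section 2.7 plans safety summaries both for the core period alone and overall.

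**The concern.** The label refers to the study, but the definition it points to stops at the core period. Because the rule takes the earliest of its candidate dates, the last core visit always wins over an end month in the extension. An event that began and ended in the extension is then closed before it began.

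At stake is the dating of extension safety records. AEs with two partial dates can change period. Wrongly early end dates also feed three other outputs: the occurrence count for safety disclosure (Section 2.7.1.2), the check that symptoms coincide with abnormal liver tests (footnote to Table 2-2), and the AE listings.

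**Working it through.** The plan states no figure on this point, so there is none to reproduce. The check applies the rules literally to example records.

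**Assumed dates (not from the documents).** First dose 10 Jan 2022. Last core visit on Day 168, which is 10 Jan + 167 days = 26 Jun 2022. Data cut-off 15 Nov 2022 (Day 310), with the participant still in contact then.

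**Rules**
- Last contact (2.1.1.5) = later of last core visit and any consent-withdrawal date.
- AE end, day missing (5.1.1.1) = min(last contact, month end, death). With month and day missing, 31 December replaces month end.
- AE start, month known, same year as first dose, month later than first dose (5.1.1.2) = max(first of month, start reference date + 1 day). The reference here is the first dose, because the imputed end is not before it. If the imputed start exceeds the imputed end, start = end.
- Medication end (5.1.2.1) = min(last contact, month or year end); if this precedes the start, end = start.

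**Step by step, AE from Sep 2022 to Oct 2022, both days missing**
1. End = min(26 Jun, 31 Oct) = 26 Jun 2022.
2. Start = max(1 Sep, 11 Jan) = 1 Sep 2022.
3. 1 Sep is later than 26 Jun, so start = 26 Jun 2022, Day 168. The event is now dated in the core period.

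**With a complete start of 12 Sep 2022 (Day 246)** the start stands and the end is 26 Jun (Day 168): 246 − 168 = 78 days before onset.

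| Record | Cap as written (26 Jun) | Whole-study cap (15 Nov) |
|---|---|---|
| AE Sep to Oct, both days missing | 26 Jun to 26 Jun (Day 168) | 1 Sep (Day 235) to 31 Oct (Day 295) |
| AE 12 Sep to Oct, end day missing | 12 Sep (Day 246) to 26 Jun (Day 168) | 12 Sep to 31 Oct |
| AE 12 Sep, end year only | 12 Sep to 26 Jun | 12 Sep to 15 Nov (Day 310) |
| AE Sep (day missing), ongoing | 1 Sep, no end | unchanged |
| AE Sep (day missing) to 5 Oct | 1 Sep to 5 Oct (Day 269) | unchanged |
| Medication Sep to Oct, both days missing | 26 Jun to 26 Jun | 1 Sep to 31 Oct |
| Medication 12 Sep to Oct, end day missing | 12 Sep to 12 Sep | 12 Sep to 31 Oct |

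**Consent withdrawn in the extension, 20 Oct 2022 (Day 284).** The cap becomes max(26 Jun, 20 Oct) = 20 Oct. The first two AE records then run from 1 Sep or 12 Sep to 20 Oct, and none of the errors occurs.

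**Where the early end date is used**
- *Disclosure count (2.7.1.2).* Consecutive events with the same term count once if the gap is at most 1 day. Suppose the same term starts again on 1 Nov (Day 296). With an end of 31 Oct the gap is 296 − 295 = 1 day, so one occurrence. With an end of 26 Jun it is 296 − 168 = 128 days, so two.
- *Liver check (Table 2-2).* A symptom is concomitant only if it starts before and stops after the laboratory date. A stop at Day 168 fails that test for any extension sample.
- *Listings.* The AE would be shown ending before it starts.

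**The case against.** The strongest reply is that the damage is narrow, and much of this stands.
- Tables of treatment-emergent AEs go by start date (Section 2.7). An AE with a complete start date therefore keeps its period.
- A moved event is still on treatment, so overall counts and overall exposure-adjusted rates do not change.
- No AE-duration summary is planned.
- Missing values are queried (Protocol Section 11.2), so partial dates should be uncommon.
- The final extension report has its own analysis document, so only extension data up to this cut-off are exposed.

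A second reply is that programmers would use the true last contact. That would depart from an explicit cross-reference, and a SAP that sets out imputation in this detail should not depend on it.

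A reader might infer that every extension AE with a partial end date is affected. The documents do not support that: AEs that are ongoing or lack an end year are not imputed, and the cap reaches into the extension for participants who withdraw consent there. A reader might also infer that medications get reversed dates, or that all those without an end date are closed the day after the core period. Rule 4 of Section 5.1.2.1 prevents reversal when the start date is complete, and ongoing medication records are not imputed.

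**Conclusion.** The rule is wrong as written. It gives an incorrect date from a stated definition, so this is more than missing detail.

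The reversal needs an AE that began in the extension, has a partial end date with the year known, is not ongoing, and belongs to a participant who has not withdrawn consent there. The change of period needs a partial start as well. Medications with a complete start in the extension shrink to one day; those with both dates partial can be moved to the last core visit.

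The 78-day figure depends on the assumed dates. The number of affected records cannot be derived from the documents. Primary efficacy is not affected.

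A reader might go further and infer that extension rescue medication would turn responders into failures in the supplementary estimand (Section 2.5.5), which counts rescue use between Day 1 and Day 168. That would need a rescue record with both dates partial, a last core visit no later than Day 168, and rule 4 not being applied to a partial start. The documents do not establish that these conditions would be met.

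**What to change.** 1. For Sections 5.1.1.1 and 5.1.2.1, define a participant-specific whole-study date of last contact: the later of the last visit or contact in the core or extension period and any consent-withdrawal date, not beyond the data cut-off. The cut-off must be a ceiling and not one of the dates in a maximum. Visits and withdrawals in the analysis fall on or before it, so a maximum that included it would always equal the cut-off, and the cap would no longer be specific to the participant.
2. Add to Section 5.1.1.1 that an imputed AE end date may not precede the known AE start date or, if the start is partial, the first day of its known month or year. The guard must use the reported start components, because Section 5.1.1.2 needs the imputed end before it imputes the start.

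The cost is two sentences in the SAP and a small programming change. No planned analysis is lost.

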5.1.1.2 AE start date imputation

Rules for imputing the AE start date:

The following table explains the notation used in the logic matrix. Please note that **missing start dates** will not be imputed.

	Day	Month	Year
Partial Adverse Event Start Date	Not used	MON	YYYY
Treatment Start Date	Not used	TRTM	TRTY

The following matrix explains the logic behind the imputation.

	MON MISSING	MON < TRTM	MON = TRTM	MON > TRTM
YYYY MISSING	(1) No convention			
YYYY < TRTY	(2.a) Before Treatment Start	(2.b) Before Treatment Start	(2.b) Before Treatment Start	(2.b) Before Treatment Start
YYYY = TRTY	(4.a) Uncertain	(4.b) Before Treatment Start	(4.c) Uncertain	(4.c) After Treatment Start
YYYY > TRTY	(3.a) After Treatment Start	(3.b) After Treatment Start	(3.b) After Treatment Start	(3.b) After Treatment Start

Before imputing AE start date, find the AE start reference date.

1. If the imputed AE end date is complete and the imputed AE end date < treatment start date then AE start reference date = min(informed consent date, earliest visit date).
2. Else AE start reference date = treatment start date

Impute AE start date -

1. If the AE start date year value is missing, the date uncertainty is too high to impute a rational date. Therefore, if the AE year value is missing, the imputed AE start date is set to NULL.
2. If the AE start date year value is less than the treatment start date year value, the AE started before treatment. Therefore:

- a. If AE month is missing, the imputed AE start date is set to the mid-year point (01JulYYYY).
 - b. Else if AE month is not missing, the imputed AE start date is set to the mid-month point (15MONYYYY).
3. If the AE start date year value is greater than the treatment start date year value, the AE started after treatment. Therefore:
- a. If the AE month is missing, the imputed AE start date is set to the year start point (01JanYYYY).
 - b. Else if the AE month is not missing, the imputed AE start date is set to the later of (month start point (01MONYYYY), AE start reference date + 1 day).
4. If the AE start date year value is equal to the treatment start date year value:
- a. And the AE month is missing the imputed AE start date is set to the AE reference start date + 1 day.
 - b. Else if the AE month is less than the treatment start month, the imputed AE start date is set to the mid-month point (15MONYYYY).
 - c. Else if the AE month is equal to the treatment start date month or greater than the treatment start date month, the imputed AE start date is set to the later of (month start point (01MONYYYY), AE start reference date + 1 day).

If complete imputed AE end date is available and the imputed AE start date is greater than the imputed AE end date, then imputed AE start date should be set to the imputed AE end date.

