2.7 Safety analyses

Unless otherwise specified all safety summaries will be presented by SAF. Safety summaries based on only core treatment period and overall (based on information from core treatment period and extension treatment period) will be produced as appropriate.

Safety summaries (tables, figures) include only data from the on-treatment period with the exception of baseline data which will also be summarized where appropriate (e.g., change from baseline summaries). In particular, summary tables for adverse events (AEs) will summarize only on-treatment events, with a start date during the on-treatment period (treatment-emergent AEs). In addition, a separate summary of death events including on treatment and post treatment deaths will be provided if appropriate.

The on-treatment period lasts from the date of first administration of study treatment to 7 days after the date of the last actual administration (including core treatment period, extension treatment period and tapering procedures after permanent treatment discontinuation) of iptacopan which covers slightly more than 5 times the estimated half-life of iptacopan.

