2.7.1 Adverse events (AEs)

All information obtained on AEs will be displayed by participant.

The number (and percentage) of participants with treatment emergent AEs (events starting after the first dose of study medication or events present prior to start of treatment but increased in

severity based on preferred term) and treatment emergent serious adverse events (SAEs) will be summarized in the following ways:

- by primary system organ class (SOC) and preferred term (PT).
- by primary SOC, PT and maximum severity.

Separate summaries will be provided for study treatment emergent AEs, death, SAEs, and AEs leading to discontinuation of study medication, and for iptacopan tapering if this is followed prior to complete study dose discontinuation. For patients receiving iptacopan, treatment emergent SAEs and AEs with PTs in the AESI 'PNH haemolysis and thrombosis' occurring after discontinuation of iptacopan 200 mg b.i.d will be reported separately.

A participant with multiple AEs within a primary SOC is only counted once towards the total of the primary SOC.

Most frequent AEs, most frequent SAEs, AEs leading to treatment discontinuation will be presented by preferred term.

Summaries presenting exposure adjusted incidence rates and associated 95% CI based on TEAEs and treatment emergent SAEs will be provided. AEs (including pre-treatment, on-treatment, post-treatment events) will be listed.

In order to address the issue of variable follow-up duration within study, the exposure adjusted incidence rate of TEAE will be presented by primary SOC and PT.

For the most common AEs, the 95% CI of the exposure adjusted incidence rate of TEAE can be presented.

Exposure adjusted incidence rate and 95% confidence interval

For summary tables on exposure-adjusted AEs, the number of episodes per 100 patient years will be presented. The occurrence rate (number of episodes per 100 patient years) will be calculated as $100 \times (\text{the total number of AE episodes from all patients in the population} / \text{the total number of patient-years})$. A patient may have multiple occurrences of the same event. All occurrences are counted. Total patient years will be computed as (sum of the duration of on-treatment periods over patients, in days)/365.25. The approximately 95% CIs for the occurrence rate will be calculated with correction for overdispersion using the asymptotically robust method ([Scosyrev 2016](#), [Scosyrev and Pethe 2022](#)).

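### An adverse event with no start year gets a NULL start date and, read literally with SAP 2.7, would be left out of the treatment-emergent tables and rates, although still listed

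*SAP*

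**What the plan says.** **Date rule.** SAP 5.1.1.2 covers partial AE start dates. Where the start year is missing, rule 1 gives as its reason that "the date uncertainty is too high to impute a rational date", and concludes: "if the AE year value is missing, the imputed AE start date is set to NULL". The corresponding row of the logic matrix reads "1) No convention". A sentence above the matrix also says that start dates that are missing are left unimputed.

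**Counting rule.** SAP 2.7 says the AE summary tables "will summarize only on-treatment events, with a start date during the on-treatment period (treatment-emergent AEs"). It defines the period as follows: "The on-treatment period lasts from the date of first administration of study treatment to 7 days after the date of the last actual administration". SAP 2.7.1 gives a second route to treatment-emergent status: "or events present prior to start of treatment but increased in" severity.

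**Neighbouring rule.** When the AE year equals the treatment-start year, rule 4.a of SAP 5.1.1.2 says: "And the AE month is missing the imputed AE start date is set to the AE reference start date + 1 day". The reference date is the treatment start date, unless a complete (imputed) end date falls before treatment start. In that case it is the earlier of the consent date and the first visit date.

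**The concern.** The date rule and the counting rule sit in different sections, and neither refers to the other. Rule 1 leaves the date empty. SAP 2.7 requires a date inside a window. A programmer who follows both as written will not count the event, and no third passage tells the programmer to do otherwise.

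This is a single-arm trial of about 40 participants, so absolute incidences and rates carry the safety description. Taken alone, rule 1 can only lower those figures, because it never adds an event. It also reverses the ordering one would expect: when less is known about onset, the default is the less cautious one.

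**Working it through.** The SAP states no figure that depends on this rule, so there is nothing to reproduce. The check applies the rules to a test case and then sizes one omitted event.

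**1. Rules side by side.** Take an AE whose complete end date falls after first dose, so that the reference date is treatment start.

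| What is missing | Rule | Imputed start | Within on-treatment window? |
|---|---|---|---|
| Month; year = treatment year | SAP 5.1.1.2, 4.a | treatment start + 1 day | Yes: counted |
| Year | SAP 5.1.1.2, 1 | NULL | Test not met: not counted |

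The worsening route in SAP 2.7.1 does not rescue the second case, because an empty start date does not establish that the event was present before treatment.

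The SAP does not treat a missing year as beyond imputation everywhere. For a concomitant medication with no start year, SAP 5.1.2.2 rule 1 imputes the day before treatment start.

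**2. What the omission touches.** It affects the treatment-emergent AE and SAE tables and the exposure-adjusted rates (SAP 2.7.1), the AESI summaries (SAP 2.7.1.1) and the disclosure tables built on treatment-emergent events (SAP 2.7.1.2). The rate denominator is the sum of on-treatment days divided by 365.25. It does not depend on AE dates, so only the numerator falls.

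**3. Size of one omission.** Assume 40 treated participants with full follow-up.

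- Incidence, if the participant has no other event in that row: 1/40 = 2.5 percentage points.
- Core-period rate: 40 × 168/365.25 = 18.4 patient-years, and 100/18.4 = 5.4 per 100 patient-years for one event.
- Core plus extension: 40 × 336/365.25 = 36.8 patient-years, and 100/36.8 = 2.7 per 100 patient-years.
- Adding the 7-day tail to each participant changes the two rates only to 5.2 and 2.7.

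**4. Where an undated onset could lie.** AEs are recorded only after consent (Protocol 10.1.1). Screening lasts up to 8 weeks, the Core period 24 weeks and the Extension 24 weeks (Protocol 3). If AEs arose at a constant rate and everyone stayed on treatment, the on-treatment share of the collection window would be 24/(8 + 24) = 75% for the Core period and 48/(8 + 48) = 86% overall. Shorter screening raises these shares. Follow-up after stopping treatment lowers them. They illustrate window length and do not estimate how many events are affected.

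**The case against.** The strongest case on the other side has five parts.

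- **The SAP never says these events are not treatment-emergent.** A reader might infer a stated exclusion, or that such an AE cannot be treatment-emergent. The documents do not go that far: rule 1 deals with the date and is silent on the flag. This stands, and it limits the point to a literal reading of two sections together.
- **The rule is deliberate and reasoned.** It is pre-specified with a rationale. That stands as a description, but the rationale does not settle the classification. Consent bounds onset from below, and the reference-date step already shows how an end date can separate events that ended before treatment from the rest. Rule 1 makes no use of either.
- **The events are not lost.** SAP 2.7.1 lists all AEs, whether pre-, on- or post-treatment, and SAP 2.7.2 lists all deaths. This stands, though a listing does not correct a count or a rate.
- **The trigger is rare.** Start dates are collected for every AE (Protocol 10.1.1), scheduled visits are at most 28 days apart, SAEs are reportable within 24 hours of awareness, and missing values are queried (Protocol 11.2). This stands. The number of such records may be zero.
- **Other rules push the opposite way.** Rules 4.a and 4.c place uncertain onsets in the treatment year after treatment start unless the end date precedes treatment, which can raise treatment-emergent counts. This also stands: the undercount belongs to rule 1 and is not shown to be the net direction of the AE tables.

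**Conclusion.** The point holds in a limited form. Read literally, SAP 5.1.1.2 rule 1 and SAP 2.7 leave an AE with no start year out of the treatment-emergent tables and rate numerators, even when its end date falls after first dose. That handling is less conservative than rule 4.a.

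A reader might also infer that the omitted events are mostly on-treatment ones. The documents do not show this. The 75% and 86% shares rest on a constant AE rate and ignore AE collection after discontinuation, which Protocol 10.1.1 continues until end of study where that is later than 7 days after last dose. An end date after first dose is also compatible with onset in screening.

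The expected effect is small. One affected participant moves an incidence by 2.5 percentage points, assuming 40 participants and no other event for that participant in the row. This is a worthwhile clarification and no threat to the safety conclusions as planned.

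**What to change.** Amend SAP 5.1.1.2 as follows.

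1. Replace rule 1. For a missing start year, classify the AE as treatment-emergent by imputing the AE start reference date plus one day, as in rule 4.a, unless the end date or other dated information shows onset outside the on-treatment period. The section already resets an imputed start that is later than the imputed end date to that end date, so no new cap is needed.
2. Bring the matrix row for a missing year, and the sentence saying that missing start dates are left unimputed, into line with the new rule.
3. Report the number of AEs classified this way, so that a reader can see whether the rule mattered.

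The cost is a short text change and a matching change to the date-imputation program. The drawback is that an occasional pre-treatment or post-treatment AE will be counted as treatment-emergent. Rule 4.a already accepts error in that direction for events of uncertain onset.
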